10.8 Statistical Review			
Name of statistician or person who prepared the statistical	Department/Institution:	Date statistical review was conducted:	
plan:		conducted:	
[name]	HART	12/19/2022	
team if they meet the definition of ke conduct, or reporting of the research If a statistical review has not been su	ı).		
11.0	Subject Pop	ulation	
11.1 Please select the population(s)	being targeted, or likely to be incl	uded in this research study. (select all	that apply)
 Normal Adults/Healthy Volunt In-Patient Population Out-Patient Population Patients in emergency situation Terminally ill patients Employees/Staff Students Children/Minors (anyone your 	ons nger than 18 years of age in th	e state of Virginia. For research	
conducted outside of the stat Prisoners Pregnant Women Fetuses Neonates of uncertain viabilit Adults with Impaired Decision	e of Virginia, age of majority is y and/or nonviable neonates n-Making Capacity proficiency (LEP) or Non-Englis	dependent on state/local law)	

11.2 Please indicate the total number of subjects anticipated to be enrolled at this site/by this investigator.

For the purposes of the IRB, a subject is enrolled once they have provided consent to participate, or for studies approved with a waiver of consent, once data has been collected on the subject.

15

11.3 If the research involves multiple subject groups or cohorts at this site, provide the anticipated number of subjects in each of group or cohort (e.g., control/experimental, adults/children, etc.).

This research does not involve multiple subject groups or cohorts.

11.4 Provide the age range for the proposed subject population (e.g., 0-5 years old):

18 and older

11.5 Specify the inclusion criteria for each of the subject groups to be included in the research.

If there are multiple different groups being recruited with different eligibility criteria, instead add an Eligibility Criteria checklist for each group as a supplemental document after you complete this application. Please make note of this in the Inclusion Criteria below.

Order Number	Criteria	
1	Patients 18 year of age or older	
2	Clinical diagnosis of lymphedema	
3	Receiving current, once weekly, lymphedema treatment by PT/OT	
4	Participants must have the ability to provide consent for themselves	

11.6 Specify the exclusion criteria for each of the subject groups to be included in the research.

If there are multiple different groups being recruited with different eligibility criteria, instead add an Eligibility Criteria checklist for each group as a supplemental document after you complete this application. Please make note of this in the Exclusion Criteria below.

Criteria
Active infection
Active cancer (not in remission)
Diagnosis of/past medical history of deep venous thrombosis or pulmonary embolism
Active phlebitis
Diagnosis of congestive heart failure
Previous severe trauma (i.e. requiring extensive corrective surgery)

7 History of vascular surgery			
8 Lesions of the skin or weeping skin in the t	eatment area		
11.7 Is information being obtained about individuals other than the "target subjects" (such as a family member or colleague of the subject), making the other individuals "secondary subjects"?			
O Yes 🖸 No			
12.0 Informed Cons	ent for Adult Subjects		
12.1 How do you plan to obtain consent from ADULT subject	or their Legally Authorized Representative?		
Check all that apply:			
Written consent document with signature (ie: obtaining Authorized Representative)	ng signature from subject or Legally		
Waiver of written documentation of consent (ie: cons confirmation from the subject or Legally Authorized R signed document)	-		
Waiver of informed consent for minimal risk research study does not involve any interaction or intervention			
Waiver or alteration of the elements of informed cons Waiver of the informed consent document and process			
Contact the IRB before submission. No adults are being enrolled; this study is only enroll			
about the assent and parental permission process lat			
You must attach all consent forms, consent scripts, and informe	tion sheets in the Initial Submission Packet.		
12.2 Is it expected that surrogate consent will need to be obtai all adult subjects?	ned from Legally Authorized Representatives (LARs) for some or		
O Yes 🖸 No			
12.3 If the research includes more than one subject group or you have selected multiple responses above due to the inclusion of multiple subject groups, please specify the requested consent method for each group, or state N/A.			
N/A			

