- 1. Prior to starting the day, the occupational therapist listed in this application will scan their clinic schedule and identify patients that meet study inclusion/exclusion criteria. This occupational therapist works at both of the locations listed above.
- 2. They will verbally bring up this research study to eligible patients during their regularly scheduled treatment visit, which is typically about an hour long. Lymphedema is treated with a combination of massage and compression, giving the occupational therapist (OT) leeway to talk to a patient while they deliver hands-on treatment. The OT will give a brief explanation of what will happen to the patient and how it will/will not impact their care.
- 3. If a patient expresses interest in participating in the study, the occupational therapist will give them an unsigned copy of the consent document to take home and read over. The OT will verbally confirm that the patient is interested in participating in this study. Additionally, the OT will confirm the patient's contact information (phone number and email address if applicable) and the best time to reach out to them. Then, the OT will reach out to a member of the research team and relay the patient's contact information.
- 4. After receiving the patient's demographics (name and DOB) from the OT, a designated member of the research team (who is Carilion Affiliated or a VTCSOM student and has been approved by the IRB) will access the patient's chart via Epic and confirm their eligibility according to the inclusion/exclusion criteria.

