- 3. If a patient expresses interest in participating in the study, their provider will give them an unsigned copy of the consent document to take home and read over. The provider will confirm that the patient is agreeable to being contacted by the research team and confirm their contact information and the best time to reach out to them. Then, the provider will reach out to a member of the research team and relay the patient's contact information.
- 4. Contact by telephone will only occur once the potential participant has been approached in person and verified interest in the study. Initial contact by phone will only occur by Carilion Affiliated or VTCSOM IRB approved team members unless the participant gives verbal permission to be contacted by a VT Team member, which will then be documented in the research record
- 5. This encounter will be documented as a research note in Epic by a member of the research team.
- 6. Two to three days after the initial contact has been made, a designated member of the research team will attempt to contact the patient via phone call, limiting the number of attempts to three. If the research team member cannot reach the patient during this time, they will not be included in the research study.
- 7. If the study team is able to make contact with the patient, they will have the option to either undergo econsent or choose to sign the consent form at their next regularly scheduled office visit. All consenting procedures will be completed by the Carilion Affiliated or VTCSOM IRB approved team members.

22.5 After potential subjects are identified, describe the pre-screening process that will take place prior to obtaining informed consent.

This could include asking questions to a potential subject to determine whether he or she meets eligibility criteria, for example: patients will answer questions about their medical history, be expected to come to the first screening visit after fasting, stop taking medications, change diet, etc. To comply with HIPAA regulations, only the minimum necessary protected health information may be collected at this time. This means only questions relating to the inclusion and exclusion criteria may be asked.

No prescreening will take place

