During the pre-screening process, patients will be asked to confirm their legal name and date of birth (to verify identity). They will also be asked to verify their past medical history, as our inclusion criteria stipulates a current diagnosis of lymphedema. Additionally, patients will be asked about their current health, as our exclusion criteria excludes patients with certain chronic conditions from participating in the research study.

22.6 Indicate whether pre-screening information will be retained on persons who do not ultimately participate in the study and what specific information, including identifiers, will be retained.

Identifiers from patients that decide to not participate in the research study will be maintained on file. This is for the sole purpose of creating a running list so that patients who are not interested in participating are not contacted more than once.

Attach all recruitment materials, letters, phone scripts, flyers, etc. in the Supplemental Documents section after you complete the IRB application.

23.0

Risks and Risk Minimization and Benefits

23.1 List the possible risks, discomforts, or harms to subjects associated with the research.

If the risks differ based on group assignment, describe for each group. Estimate the (1) probability of occurrence, (2) the seriousness, and (3) the duration of each risk. If this information is captured in the protocol or investigators brochure (IB) or other materials, indicate the document and page numbers where the information can be located.

Possible risks, discomforts, or harms include:

Physical: The pressure of the device is less than that of an inflated blood pressure cuff. It is most comparable to a blood pressure cuff that has been well-fitted, but has not been inflated. The device utilizes a level of vibration that has been demonstrated to be similar to devices currently in use by lymphedema therapists. Please see this **link** for a commercially available vibrator that is similar to what is typically used.

- Skin tingling sensation
 - Skin tingling sensation is a common occurrence, but it is mild and will subside after treatment has ended.
- Pain, soreness, or swelling
 - Pain, soreness, or swelling is an uncommon occurrence, but it is mild and will subside after the device is removed and treatment has ended.
- Dizziness
 - Dizziness is an uncommon occurrence, but it is mild and will subside after treatment has ended.
- Headache

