For this study, a Data Safety and Monitoring Committee (DSMC) will be established. The committee consists of a physician, lymphedema therapist, and biomedical engineer. They will be familiar with the project, but will have no direct involvement in it. The DSMC will review any reports of anticipated side effects, unanticipated side effects, serious adverse events and unanticipated problems. The study population consists of 15 subjects. Routinely, after each of the first 2 cohorts of 5 study subjects each, the DSMC will conduct a review. The DSMC will only have access to de-identified data. Until this review is completed, and the DMSC makes a recommendation to continue, no subjects will be enrolled and studied. The DMSC will make its determinations based upon review of data that includes the incidence of side effects (physical risks and harms outlined in section 23.1) and incidence of adverse events and serious adverse events (outlined in section 23.2) For occurrence of any unanticipated side effects or adverse events, the study will be immediately suspended, and these conditions will be reviewed by the DSMC, followed by reporting to the IRB. The study will only continue if recommended by the DMSC and permitted by the IRB. Data that will be provided to the IRB if the Stop/Pause is activated will be submitted in writing, and include full disclosure of all data collected, and any written annotations associated with the study in the patient chart. A recommendation of whether the study should continue without modification, continue with modification, or no longer continue from the DSMC will be provided to the IRB in writing after each meeting is held.

23.7 Describe the plans and rationale for conducting an interim analysis.

🔿 Yes 💿 No

23.8 Have stopping rules been established for the study, including for reasons of futility?			
⊙ Yes ○ No			
Describe the stopping rules:			
If any of the following were to occur during the course of the research study, the study will be discontinued.			
 Bleeding or bruising Interference with electronic devices such as, but not limited to, hearing aids and mobile phones Any evidence of increasing edema with use of the device 			
23.9 Are there defined criteria (ex: rates of adverse events) for when study interventions should be discontinue	d?		
⊙ Yes ○ No			
Describe the criteria:			
If any of the following were to occur during the course of the research study, the study will be discontinued.			

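### Bleeding or bruising and electronic interference each end the study, yet no eligibility criterion or listed baseline item asks about bleeding disorder, anticoagulant use or implanted electronic devices

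*Combined protocol and SAP*

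**What the plan says.** Section 23.8 sets the consequence: "If any of the following were to occur during the course of the research study, the study will be discontinued". Three events follow: "Bleeding or bruising"; "Interference with electronic devices such as, but not limited to, hearing aids and mobile phones"; and "Any evidence of increasing edema with use of the device". Section 23.9 repeats the list. Only the edema item is tied to the device. The other two carry no condition on number, severity or cause.

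Sections 11.5 and 11.6 give four inclusion and eight exclusion criteria. The exclusions nearest to the point are "Diagnosis of/past medical history of deep venous thrombosis or pulmonary embolism", congestive heart failure and earlier vascular surgery.

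Screening follows the criteria. Under 22.2 a team member opens the chart to "confirm their eligibility according to the inclusion/exclusion criteria". Under 22.5 patients verify their past medical history, which the text links to the lymphedema diagnosis, and "patients will be asked about their current health, as our exclusion criteria excludes patients with certain chronic conditions". The form's own instruction in 22.5, which covers the period before consent, adds: "This means only questions relating to the inclusion and exclusion criteria may be asked".

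Section 18.3 lists four things to collect: arm circumference, induration, the first part of the Lymphedema Life Impact Scale (LLIS), and side or adverse effects.

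**The concern.** The sponsor regards two events as grave enough to end the study. The natural counterpart is to ask beforehand who is prone to them. As written, a patient who takes an anticoagulant for a reason other than a past clot, or who has an implanted device without heart failure, meets every criterion. Such a patient can reach the first session without any step shown having required someone to consider the matter.

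Two things are at stake. The first is a considered decision before exposure, in what section 10.7 describes as the device's first use in patients. The second is context afterwards: the DSMC works from de-identified data and must advise whether to continue, modify or stop. It would be helped by knowing whether the participant who bruised was on an anticoagulant. A chart look-up after the event could recover some of this, but too late for a decision before first use. Neither event appears among the risks in 23.1 or the adverse events in 23.2, so the stopping rule is the only place shown that deals with them.

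**Working it through.** The plan gives no figure of its own on this point: no event rate, and no count of patients with either exposure. The check is therefore a comparison of sections, with counts.

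1. **Stopping events (23.8).** There are three items, of which one is worded as occurring with device use. 3 − 1 = 2 have no such tie: bleeding or bruising, and electronic interference.
2. **Eligibility (11.5, 11.6).** 4 inclusion + 8 exclusion = 12 criteria. Number naming bleeding disorder, anticoagulant use or an implanted electronic device: 0 of 12. The clot, heart failure and vascular surgery exclusions remove some of these patients, but only incidentally.
3. **Screening (22.2, 22.5).** The chart check is made against the 12 criteria. The verbal check covers past history and current health for the sake of the same criteria. A bleeding disorder or implant might be mentioned or seen, but no criterion says what to do about it. The form's limit on questions applies only before consent. Staff could ask later, but no step shown tells them to.
4. **Recording (18.3, 18.1 step 3, 15.4).** Four items are listed, and 0 of 4 is a history, medication or implant item. The pre-device step in 18.1 adds none. Section 15.4 points to the data collection tool, which is not shown.
5. **Opportunities for an event.** 15 participants (11.2) × 4 weekly visits (18.4) = 60 visits. One event at any of them meets the rule as worded.
6. **How sensitive the rule is, on assumed rates only.** Let p be the chance per visit of a triggering event, taken as equal and independent across visits. Then P(at least one) = 1 − (1 − p)^60.
   - p = 0.1%: 1 − 0.999^60 = 5.8%
   - p = 1%: 1 − 0.99^60 = 45.3%
   - p = 5%: 1 − 0.95^60 = 95.4%

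Step 6 describes the stopping rule, not this gap. The range is too wide to say how often the rule would be met. The documents do not say how many eligible patients have either exposure, so the effect of screening on these figures cannot be estimated.

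**The case against.** The strongest reply is that the remedy leaves the sharpest feature alone. With both baseline fields filled in, one bruise of any cause still stops the study. That is true. A reader might infer that screening would protect the study from an early stop, but the documents give no basis for that, and changing the rule would be a separate matter. A sensitive rule in 15 patients is also a defensible cautious choice.

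A reader might also infer that a bruise could not be attributed at all. The documents do not support this. In 18.1 there is one side-effect question straight after the device (step 5) and another after standard care. The arm is measured before the device, after it, and after standard care. The cupping in the typical session is on the side of the trunk, away from the sleeve. On a stop or pause, the IRB receives all collected data and study-related chart notes (23.6). What remains unclear is a bruise noticed after the visit, because massage and vibration tools are also used on the arm.

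Third, implants are not named in 23.8, and 23.1 describes the vibration as similar to that of devices therapists already use. This lowers the likely hazard. The item still stands, because the sponsor itself foresees interference and its list is expressly open.

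Finally, the treating therapist selects patients from their own caseload, general history is verified, and the consent form, data collection tool, training content and any device manual are not shown. It would be wrong to conclude that nobody would know or ask. What stands is narrower: nothing shown requires the question or acts on the answer.

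**Conclusion.** The gap is real and modest. Two of the three study-ending events have no matching screening step: 0 of 12 criteria and 0 of 4 listed data items address either exposure. The added hazard is probably small. Participants are already in weekly hands-on treatment, the device presses about as much as an uninflated blood pressure cuff (23.1), and clinically trained staff oversee each session (23.3). No probability is claimed.

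The conclusion rests on the sections shown and on reading the open list in 23.8 as covering implanted devices. It would shrink to a missing cross-reference if an attachment already asks these questions. The change is worth making because it costs little. It does not depend on showing that the study is unsafe as it stands.

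**What to change.** Add two items to 11.6, so that the existing checks in 22.2 and 22.5 pick them up: (a) bleeding disorder or current anticoagulant use; (b) implanted or otherwise non-removable electronic medical device. Neither need exclude automatically. Each should require documented investigator clearance before the first session, with a line stating what the investigator is to weigh.

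Record both as yes/no at baseline, in the de-identified data available to the DSMC. If the data collection tool, consent form, training material or device manual already asks, cite it in 11.6 instead.

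Do not require hearing aids or phones to be removed routinely, since that would hide the interference the rule is meant to detect.

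The cost is two questions within checks already performed, two data fields, and possibly an occasional deferred or declined participant out of 15. No extra visit, test or change in sample size is needed.

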12.4 How will written consent be documented?			
Click the Help bubble to the right for more informa eConsent before selecting this option.	tion about requirements for		
✓ Traditional signed written consent form on paper doc			
 eConsent: signed via an REDCap or other electronic of Short Form Method (for non-English speaking subject 			
C Other			
12.5 Describe the process of obtaining consent and documenting the process, including the following:			
approached;	ned, including how the potential participant will first be		
 Where the consent process will take place (ex: in etc.); When the consent process will take place and how 	person in a private clinic room, over the phone, through WebEx,		

- If eConsent is being utilized, describe how you will first contact the potential participants and provide the consent form to them to review;
- Steps that will be taken to ensure voluntary participant and to minimize the possibility of coercion or undue influence;
- Any cultural considerations (ex: tribal or group permission requirements, age of majority, technological implications, etc.);
- If any participants do not speak English, whether a translator with witness will be used, whether translated materials will be used, whether the consent process changes based on the language;
- If multiple participant groups or consent procedures are to be included, these need to be clearly delineated;
- how participants will be provided with a copy of their signed consent;
- Describe the method you will use to document the consent PROCESS within each participants' research record /medical record (state which). This should include a process note or checklist that will document all the components listed above, the start and end time of the discussion, and is in addition to the signed and dated consent form (if applicable).

For example, describe it consent will take place in the research office, in a private conference room, in the doctor's office, in a group setting, over the phone, etc.

GENERAL

- The occupational therapist (OT) listed at the beginning of this application will identify potential participants (based on established inclusion and exclusion criteria) from their patient pool. All consenting procedures will be completed by the Carilion Affiliated or VTCSOM IRB approved team members.
- 2. The occupational therapist will verbally bring up this research study during a patient's regularly scheduled treatment visit, which is typically about an hour long. Lymphedema is treated with a combination of massage and compression, giving the OT leeway to talk to a patient while they are delivering hands-on treatment. They will give a brief explanation of what will happen to the patient and how it will/will not impact their care. Only the occupational therapist will initially approach potential subjects.
- **3.** If a patient expresses interest in participating in the study, the OT will give them an unsigned copy of the consent document to take home and read over. The OT will confirm their contact information and the best time to reach out to them. Then, the OT will reach out to a designated IRB approved research team member.
- **4.** This encounter will be documented as a research note in Epic by a designated IRB approved research team member.
- **5.** Two to three days after the initial contact has been made, a designated IRB approved research team member will attempt to contact the patient via phone call, limiting the number of attempts to three. There will be no voicemail left. If the designated IRB approved research team member cannot reach the patient during this time, they will not be included in the research study.
- **6.** If the designated IRB approved research team member is able to successfully make contact with the patient, they will first confirm the patient's identity by asking them to state their name and date of birth. This will create a passcode based on known information (first two letters of legal first name followed by first two letters of legal last name followed by last 2 digits of birth year). Each section of the consent form will be reviewed in detail before consent is obtained. The designated IRB approved research team member will ask the patient if they have any questions about the study.
- After the patient has expressed interest in the study and agreed to participate, they will be allowed to choose whether they would like to undergo consent in person, at their next regularly scheduled office visit or remotely, via eConsent.

IN PERSON

- 1. Upon arriving to their next regularly scheduled office visit, the patient will be brought back to a private treatment room by a designated IRB approved research team member.
- An IRB Research team member will review the each section of the consent in detail with the participantThe patient will be asked if they have any further questions about the research study.
- **3.** A number of teach-back and open-ended questions will be used to assess patient understanding regarding the research study and what is/is not expected of them. Once all applicable questions have been answered/addressed, the patient will physically sign a two paper copies of the consent form (one for the research team and one for themselves)

- 4. The participant will immediately receive their signed copy of the consent form.
- A summary of the conversation, any pertinent questions that were addressed during the encounter, and the signed consent form will be recorded in a research note in Epic. Specifically, the following points will be recorded in the research note:
 - The method that was used to discuss the study with the potential subject (discussion happened in person)
 - The questions that the potential subject asked
 - The time the potential subject was given to make their decision
 - How long the conversation lasted
- 6. Research tasks will only be completed after the informed consent document is signed.

eCONSENT

- 1. The eConsent process will take place over the phone. The patient will be asked whether they would prefer to get the link to the eConsent form emailed or texted to them.
- 2. Once communication modalities have been confirmed, the designated IRB approved research team member will have to state the following: "Carilion Clinic cannot control the security of email or text messages once we send them, therefore we need your permission to text or email you the link to the eConsent form for the study we discussed. Please be aware that while the email title will not include your lymphedema, the body of the email will contain the link to the study. Someone else accessing your email/text messages could click on the link and read the consent, and therefore learn about your lymphedema, which you may consider to be of a private or sensitive nature. Do you still wish to receive the link to the eConsent via email/text?"
- 3. The patient will receive the link via their preferred modality and review it.
- 4. An IRB Research team member will review the each section of the consent in detail with the participant. The patient will be asked if they have any further questions about the research study.
- 5. A number of teach-back and openended questions will be used to assess patient understanding regarding the research study and what is/is not expected of them.
- 6. The subject will type their name and date and use their finger, cursor, or stylus (if it is available to them) to sign in the signature field.
- 7. The participant will receive a copy of their signed consent form via email or in person at their next regularly scheduled visit.
- 8. If the patient elects to receive a copy of their consent form via email, the designated IRB approved research team member will verbally state, "Carilion Clinic cannot control the security of email messages once we send them, therefore we need your permission to email you the copy of your signed consent. Please be aware that while the email title will not include your lymphedema the attachment to the email will contain study consent. Someone else accessing your email messages could click on the attachment and read the consent, and therefore learn about your lymphedema, which you may consider to be of a private or sensitive nature. By providing your email address, you are authorizing Carilion Clinic to email you a copy of your signed form." If a signed copy of the consent will be emailed to the subject using REDCap, the subjects must provide their e-mail address on the completion page, and the following statement will be included in the field where the email address is "Enter your email to receive confirmation message? A confirmation email is supposed to be sent to all respondents that have completed the survey, but because your email address is not on file, the confirmation email cannot be sent automatically. If you wish to receive it, enter your email address below."
- 9. A summary of the conversation, any pertinent questions that were addressed during the call, and the signed consent form will be recorded in a research note in Epic. Specifically, the following points will be recorded in the research note:
 - The method that was used to discuss the study with the potential subject (discussion happened over the phone)
 - The questions that the potential subject asked

- The time the potential subject was given to make their decision
- How long the conversation lasted
- The process of verifying the individual's identity over the phone and then with the eConsent signature, as described above
- 10. Research tasks will only be completed after the informed consent document is signed.

12.6 How will you ensure that subjects or LARs have sufficient opportunity to consider whether or not to participate? Check all that apply: Subjects will be provided the consent form to take home for consideration prior to signing. Subjects will be allowed a waiting period to consider their decision. C Other Please specify waiting period: 2 to 3 days 12.7 How will the subjects' or LARs understanding of the consent information presented be assessed? Check all that apply: Subjects will be asked to "Teach-Back" the study to the researchers Subjects will be asked open-ended questions about the research (purpose, procedures, risks, alternatives, voluntary nature) A tool or post-consent assessment will be used Other Specify the "teach back" questions or open-ended questions that the subject will be asked to describe in their own words in order to assess their understanding. Open-ended Questions: • Can you please describe the study in your own words? • What would you have to do if you decide to participate in the study? • Is there anything that you can or can not do while participating in this study? • How long will your participation in the study be? Multiple Choice Questions: • What will you do as part of the study? • Wear an investigational device as part of my therapy • Receive no therapy at all • Only complete surveys • None of the above • I am able to withdraw from the study at any point in time. • True False • I will be asked to attend my appointments more frequently as a result of my participation in this study. • True • False

12.8 Utilizing eConsent has additional requirements. Please describe the following:

- The method to verify the identity of the individual providing consent;
- How participants will sign the eConsent (ex: type their name, use stylus or finger to sign);
- If potential participants will sign the consent while having a virtual conversation or if they will have additional time to consider their participation;
- If use of LAR is being requested, how you will ensure this individual is an appropropriate LAR per Virginia requirements and verify their identity.
- The occupational therapist (OT) listed at the beginning of this application will identify potential participants (based on established inclusion and exclusion criteria) from their patient pool. All consenting procedures will be completed by the Carilion Affiliated or VTCSOM IRB approved team members.
- 2. The occupational therapist will verbally bring up this research study during a patient's regularly scheduled treatment visit, which is typically about an hour long. Lymphedema is treated with a combination of massage and compression, giving the OT leeway to talk to a patient while they are delivering hands-on treatment. They will give a brief explanation of what will happen to the patient and how it will/will not impact their care. Only the occupational therapist will initially approach potential subjects.
- 3. If a patient expresses interest in participating in the study, the OT will give them an unsigned copy of the consent document to take home and read over. The OT will confirm their contact information and the best time to reach out to them. Then, the OT will reach out to a designated IRB approved research team member.
- 4. This encounter will be documented as a research note in Epic by a designated IRB approved research team member.
- 5. Two to three days after the initial contact has been made, a designated IRB approved research team member will attempt to contact the patient via phone call, limiting the number of attempts to three. There will be no voicemail left. If the designated IRB approved research team member cannot reach the patient during this time, they will not be included in the research study.
- 6. If the designated IRB approved research team member is able to successfully make contact with the patient, they will first confirm the patient's identity by asking them to state their name and date of birth. This will create a passcode based on known information (first two letters of legal first name followed by first two letters of legal last name followed by last 2 digits of birth year). Each section of the consent form will be reviewed in detail before consent is obtained. The designated IRB approved research team member will ask the patient if they have any questions about the study.
- 7. After the patient has expressed interest in the study and agreed to participate, they will be allowed to choose whether they would like to undergo consent in person, at their next regularly scheduled office visit or remotely, via eConsent.

eCONSENT

- 1. The eConsent process will take place over the phone. The patient will be asked whether they would prefer to get the link to the eConsent form emailed or texted to them.
- 2. Once communication modalities have been confirmed, the designated IRB approved research team member will have to state the following: "Carilion Clinic cannot control the security of email or text messages once we send them, therefore we need your permission to text or email you the link to the eConsent form for the study we discussed. Please be aware that while the email title will not include your lymphedema, the body of the email will contain the link to the study. Someone else accessing your email/text messages could click on the link and read the consent, and therefore learn about your lymphedema, which you may consider to be of a private or sensitive nature. Do you still wish to receive the link to the eConsent via email/text?"
- 3. The patient will receive the link via their preferred modality and review it.
- 4. An IRB Research team member will review the each section of the consent in detail with the participant. The patient will be asked if they have any further questions about the research study.
- 5. A number of teach-back and open-ended questions will be used to assess patient understanding regarding the research study and what is/is not expected of them
- 6. The subject will type their name and date and use their finger, cursor, or stylus (if it is available to them) to sign in the signature field.
- 7. The participant will receive a copy of their signed consent form via email or in person at their next regularly scheduled visit.

